3.2. Phase 2: CPM-DA FEASIBILITY TRIAL (Months 17-24)

The primary goal is to evaluate whether women will participate, use the DA, and evaluate the DA positively. A second goal is to gather pilot information about the impact of the DA on knowledge, psychological constructs, decisional conflict, and preparedness. We will conduct a small randomized trial assigning patients to receive Usual Care or the CPM-DA.

3.2.1. Phase 2 Inclusion criteria:

1. Completed initial surgical consult with breast cancer surgeon at CINJ/MGH/MSKCC and is considering CPM, regardless of the surgical treatment of their primary breast cancer (lumpectomy/mastectomy).
2. Has home internet access.
3. Has a first, primary diagnosis of unilateral Stage 0, 1, 2, or 3a breast cancer or Stage 1-3b who is down-staged to Stage1-3a with neo-adjuvant chemotherapy
4. ≥ 18 years
5. Speaks and reads English
6. WSC [does not have hereditary breast/ovarian cancer syndrome (BRCA carrier, strong family history)]. If there is any uncertainty, the surgeon will use the Tyrer-Cuzick (Tyrer et al., 2004) risk model to calculate risk. For this study, anyone with a lifetime risk up to 19% on the Tyrer-Cuzick model will be considered average risk for breast cancer. Anyone with a lifetime risk of 20% or greater will be excluded from participation.
7. Able to provide meaningful informed consent.

3.2.2. Phase 2 Participant Recruitment and Consent Procedures. Staff will identify women scheduled for a surgical consultation. Because this study targets women considering CPM, participants will be approached after the consult as the surgeon discusses options the patient is eligible for at this time. The surgeon will refer the patient if she is considering CPM. The project coordinator or designated study staff will review eligibility with the surgeon and medical staff, and, if the patient meets eligibility, provide an explanation of the study and cover all of the aspects of the consent with the patient.

FOR CINJ patients, they have 2 options to complete consent. They can sign paper consent or acknowledge consent before beginning an electronic survey. Participants will be given the option to complete the baseline and follow-up surveys electronically through Rutgers Population Science Datstat Illume Survey Software, via paper and pencil, or over the phone with research staff. If the participant prefers to complete a paper and pencil version of the survey, they will sign paper consent and be provided with the survey to complete in clinic. The baseline survey should take 15-20 minutes to complete. The research staff will collect the completed survey from the participant. Participants who are unable to complete the survey in clinic will be able to take the survey home to return via pre-paid mail or via email/fax. Participants will also be given the option to complete electronic surveys. Email will be required to route electronic surveys, but email is already collected for use with the B-Sure Decision Support Aid. For those patients wishing to complete the electronic baseline survey, the participant will be asked to acknowledge consent prior to beginning the survey. After consent and baseline survey are received, the participant will be randomly assigned to either the Usual Care or the CPM-DA arm. An email will be sent and/or a phone call will be placed to the participant from Rutgers CINJ staff notifying the participant of her random assignment. Usual Care is described below. Participants in the CPM-DA arm will be given their random assignment, the website address, a secure username & password, and website instructions delivered via email or paper and/or phone. The DA will be optimized to be accessible on desktops. We will email/text this same information as a reminder to participants to use the DA. Follow-up surveys will be delivered via paper and pencil, phone or electronically depending on patient preference.

For Memorial Sloan Kettering patients, all participants are required to sign paper consent forms. They will be given the option to complete the baseline and follow-up surveys electronically through Rutgers Population Science Datstat Illume Survey Software, via paper and pencil, or over the phone with research staff. If the participant prefers to complete a paper and pencil version of the survey, they will sign paper consent and be provided with the survey to complete in clinic. The baseline survey should take 15-20 minutes to complete. The research staff will collect the completed survey from the participant. Participants who are unable to complete the survey in clinic will be able to take the survey home to return via pre-paid mail or via email/fax. Participants will also be given the option to complete electronic surveys. Email will be required to route electronic surveys, but email is already collected for use with the B-Sure Decision Support Aid. For the electronic baseline survey, the participant will again acknowledge consent by beginning the survey- they will have already signed the paper consent as well. After consent and baseline survey are received, the participant will be randomly assigned to either the Usual Care or the CPM-DA arm. An email will be sent and/or a phone call will be placed to the participant from Rutgers CINJ staff notifying the participant of her random assignment. Usual

Care is described below. Participants in the CPM-DA arm will be given their random assignment, the website address, a secure username & password, and website instructions delivered via email or paper and/or phone. The DA will be optimized to be accessible on desktops. We will email/text this same information as a reminder to participants to use the DA. Follow-up surveys will be delivered via paper and pencil, phone or electronically depending on patient preference.

For Massachusetts General Hospital patients, all participants are required to sign paper consent forms prior to verifying eligibility. They will be given the option to complete the baseline and follow-up surveys electronically through Rutgers Population Science Datstat Illume Survey Software, via paper and pencil, or over the phone with research staff. If the participant prefers to complete a paper and pencil version of the survey, they will sign paper consent and be provided with the survey to complete in clinic. The baseline survey should take 15-20 minutes to complete. The research staff will collect the completed survey from the participant. Participants who are unable to complete the survey in clinic will be able to take the survey home to return via pre-paid mail or via email/fax. Participants will also be given the option to complete electronic surveys. Email will be required to route electronic surveys, but email is already collected for use with the Decision Support Aid. For the electronic baseline survey, the participant will again acknowledge consent by beginning the survey- they will have already signed the paper consent as well. After consent and baseline survey are received, the participant will be randomly assigned to either the Usual Care or the CPM-DA arm. An email will be sent and/or a phone call will be placed to the participant from Rutgers CINJ staff notifying the participant of her random assignment. Usual Care is described below. Participants in the B-Sure CPM-DA arm will be given her random assignment, the website address, a secure username & password, and website instructions delivered via email or paper. The DA will be optimized to be accessible on desktops. We will email/text this same information as a reminder to participants to use the DA. Follow-up surveys will be delivered via paper and pencil, phone or electronically depending on patient preference

Participants will be asked to complete a total of 3 surveys. Surveys will be administered via paper, online through an email link to the survey sent by Rutgers Population Science Datstat Illume Survey Software, or via phone with research staff. The baseline is administered when participants first enter the study, follow-up survey #1 is to be completed at the time of a post-op appointment, usually between 2-4 weeks after surgery and follow-up survey #2 is to be completed 6 months after the baseline survey. For both follow-ups, participants will be sent a link to the survey via email or they may also be contacted by telephone to complete the follow-up surveys. If requested, we can mail a copy of the follow-up survey to participants with a pre-paid envelope to return the survey. For follow-up #1 research staff will provide the participant with the follow-up survey at an appointment. The participant can complete the survey in clinic or they can take it home to return via mail in a pre-paid envelope. For patients who indicated a preference to complete the follow-up survey electronically, research staff will visit the participant at her appointment and remind her that the survey will be sent via email link. If patients take the survey home or prefer electronic surveys, staff will contact participants weekly and, if contact is not made within two weeks, the participant may be considered a survey refuser or drop. If participants skip the first follow-up survey, we will still send them the second follow-up survey at 6 months. We allow participants access to the website for the study duration. We do not anticipate that they will view the B-Sure website simply to look up answers for the follow-ups.

We will track website use to evaluate this possibility. Participants are paid \$25 for each survey they complete for a total of \$75. Rutgers Cancer Institute of New Jersey will provide payments to MSKCC participants in the form of gift cards which will require Rutgers staff to receive contact information (including names, address, email and phone #s) for MSKCC participants. MSKCC study consent will detail that Rutgers CINJ staff will receive their contact information to carry out study procedures. Research recruiters and site investigators [name], [name] and [name] will meet bi-weekly to review study accrual and troubleshoot enrollment challenges.

Randomization Procedures: This is a randomized trial with a Usual Care and the CPM-DA condition. Patients will be assigned to condition after consent is acknowledged online or paper consent is signed and online or paper baseline packets have been completed. A Rutgers CINJ statistician will design a blocked randomization scheme and will also ensure that randomization procedures are being followed. To randomize a new patient at Rutgers Cancer Institute of New Jersey, Memorial Sloan-Kettering Cancer Center, or Massachusetts General Hospital the following procedure will be followed: Site staff will notify the coordinator at the main site (Rutgers) when a new consent and baseline have been received. The Rutgers coordinator or appropriate study staff will randomize from the master file in the order in which notification of a new consent/baseline packet was received. The master file will be updated and research staff at all sites will be notified of the randomization. Rutgers study staff will notify participants of their randomization via email or a phone call. If applicable, Rutgers staff will provide participants with the CPM-DA website address, a secure password, and website navigation instructions. MSKCC will request to collect limited data in the form of a patient refuser form that will cause no more than minimal risk to patients that decide not to participate in MSKCC protocol #16-1396. The refuser form contains no PHI. This refuser form will be completed by the research team after approaching a patient in clinic that declines to participate in the study. The refuser form will then be sent to the sponsor site, Rutgers, to help them collect information on the feasibility of patients utilizing the decision aid and the common reasons for which patients decline to participate. The data in this form will be stored in a database at Rutgers.

For enrolled patients who ultimately seek surgery at an outside institution, the recruitment script and random assignment notification documents will inform participants that they are welcome to continue on with the study by evaluating the website if applicable and by completing the follow-up surveys. Rutgers CINJ staff will make contact with the participant to obtain the date of surgery for coordination of follow-up survey schedule.

CPM Decision Aid Arm Debriefing.

Staff at Memorial Sloan Kettering Cancer Center or Massachusetts General Hospital will contact current and former participants from the B-sure decision aid arm to obtain consent to be contacted for the debriefing interview call. After consent is received, [name] or designated Rutgers Cancer Institute of New Jersey staff member will then contact participants to schedule and conduct the brief phone interview to obtain feedback on the Decision Aid. The interviewer will remind participants of the information included in each of the B-Sure decision aid modules. The interviewer(s) will elicit feedback on the most helpful aspects of the decision aid, changes, and/or additional information that would be helpful to incorporate in future iterations of the decision aid and will also discuss the patient's decision-making process. The CPM participant Interview script along with the open-ended questions is submitted to IRB for review.

Procedures for contacting former participants/conducting interviews at Memorial Sloan Kettering Cancer Center and Massachusetts General Hospital are as follows: Participants who actively

dropped out or refused further participation in the study will not be contacted. All living participants who were randomized to the DA arm who completed all aspects of the study will be approached for the debriefing interview by the recruiting institution. The recruiting institution will send a letter explaining the purpose of the debriefing component along with the updated consent form containing optional study aspects portion. Participants will also be given a phone # and email address from the site they were recruited (MSKCC or MGH) to contact to have the consent discussion or if they want to refuse participation. Participants can mail the consent back to the recruiting institution in a pre-paid envelope. Once consent is received, Rutgers study staff will contact participants via phone to explain the study and confirm their interest in participating. A tentative date for the interview will be established. Staff will confirm that all participants have signed consent, and that the consent has been returned to Rutgers staff before conducting the interviews.

3.2.3. Sample Size for RCT. We anticipate we will recruit participants for about 6months (months 17-22). Our goal is to enroll 90 to 130 women (65 in UC and 65 in CPM DA). We are anticipating a 70-75% acceptance rate based on our BRDA study. To obtain $N = 130$ (90 MSKCC, 10 CINJ, 30 MGH), we estimate approaching 169-182 women. Because acceptance rates are a study goal, this is only an estimate, and thus we allow 6-12 months for accrual.

3.2.4 Usual Care. Usual care consists of what traditionally occurs at both sites. At both sites, the surgical oncologist educates WSC regarding the facts about CPM, including the fact that it is not medically indicated, and does not reduce the risk of the spread of cancer. If interested, the patient is referred to a plastic surgeon.

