4.1. Measures

A preliminary overview of the study measures is shown in Table 1. We will utilize concise, psychometrically valid measures used in our prior research or that of other research groups.

	Baseline	FU 1 (Around post- op appointment 2-4 weeks post-surgery)	FU 2 (6 months)
Background Variables			
- Sociodemographic characteristics	✓	---	---
- Knowledge of CPM	✓	✓	✓
Psychosocial Factors	✓	✓	✓
- Risk Perception	✓	✓	✓
- Reasons for CPM	✓	✓	✓
- Self-Efficacy	✓	✓	✓
- Social influence	✓	---	---
- Importance of Input	✓	✓	✓
Decision Factors	✓	✓	✓
- Satisfaction with/Completeness of Preparation	✓	✓	✓
- Decision Conflict	✓	✓	✓
- Interest/Intention	✓	✓	✓
Process Evaluation of DA (DA arm only)	---	✓	---

4.1.1 Baseline survey (15-20 m).

4.1.2. Demographics. Basic demographics and technology skills will be assessed.

4.1.3. Knowledge. 11-items evaluate CPM knowledge ([name], personal comm., September, 2013).

4.1.4. Psychosocial factors. 1) *Risk perception*- 3 items estimate risk for breast cancer in the other breast and how much CPM reduces risk (Rosenberg et al., 2013); 2) *Reasons for CPM*-11 reasons (Rosenberg et al., 2013); will be assessed; 3) *Self-efficacy*-3 items assess confidence in managing worry about cancer recurrence, complying with surveillance, and worry about surveillance. 4) *Social influence*- Item asks how much doctors talked about reasons to have/not have CPM; 5) *Importance of input*-Items ask how important input from surgeon, nurse, family/friends, internet, media is in the decision (Rosenberg et al., 2013).

4.1.5. Decision factors: *Satisfaction with/completeness of preparation.* The Satisfaction with the Decision-making Process Survey (Barry et al., 1997) assesses satisfaction with a number of factors including the amount of information, how information was presented, and how prepared they are to make a decision.

4.1.6. Decisional conflict. The Decisional Conflict Scale (Anderson, 2009) is a widely used scale. CPM interest/intention. Made a CPM decision; if not, rate CPM intentions.

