4.2. Follow-up Measures

4.2.1. Follow-up surveys (20m). All baseline measures except demographics will be given.

4.2.2. Process Evaluation: 1) *DA Evaluation* (DA arm only). Ratings include: extent that they used the DA, comprehensiveness of information, whether it presented material in a balanced manner, whether it influenced the decision, whether it was helpful in making the decision, whether it was helpful in understanding pros and cons, and whether they used the information in a discussion with the surgeon. Items are based on Brug (Brug et al., 2005) and previous research ([name] et al., 2010; [name] et al., 2005) 2) *DA implementation evaluation.* We will assess: a) log ins and time in DA; b) time spent in each module; c) number of pages printed out/sent to mobile device; d) ease of accessing and navigating the web-based application at home or at the center; 3) *User Interface Satisfaction* (Lund, 2001) assesses usefulness, ease of use, ease of learning and satisfaction with online tools. Feedback will be collected at the time of the first follow-up survey, but we may also contact participants by phone for a short debriefing on their experience with the site.

4.2.3 Risk and procedures for handling adverse events.

This study involves research presenting little risk. There are no physical risks or side effects associated with participation. If the participant is experiencing any psychological distress, as reported by the patient to the study staff, the study project coordinator will inform [name]. [name] will then determine if contacting the participant is necessary and/or helpful to evaluate distress levels and refer if further assistance is needed or requested. There are psychosocial resources available for patients. These procedures have been implemented successfully with our previous psychological intervention trials.

4.2.3.1. Adverse Events: In the proposed study, we define adverse events as psychological distress by the method outlined above, the following procedure for handling this event are: 1) the site PI will inform the IRB about the event; 2) the PI, [name], will be informed and this event will be reported to the Rutgers Cancer Institute of New Jersey IRB.

As with all research that collects protected health information, there is a risk that participants' confidentiality could be compromised during the study.

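### The exploratory knowledge comparison could favour the decision aid: its website stays open during unsupervised follow-up surveys, and a DA-only reminder call before the 6-month survey is not ruled out

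*Combined protocol and SAP*

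**What the plan says.** **Access.** Section 3.2.2 gives the website to one arm: "Participants in the CPM-DA arm will be given their random assignment, the website address, a secure username & password". It leaves access open for as long as the study runs.

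**Test.** Section 4.1.3 says "11-items evaluate CPM knowledge". Section 4.2.1 says of the follow-up surveys: "All baseline measures except demographics will be given". Knowledge is therefore measured at follow-up 1 (about 2 to 4 weeks after surgery) and follow-up 2 (6 months after baseline). Surveys may be done on paper, by email link or by phone, and the paper form for follow-up 1 may be filled in at the clinic or taken home.

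**Look-up.** Section 3.2.2 states: "We do not anticipate that they will view the B-Sure website simply to look up answers for the follow-ups". The next sentence says that website use will be tracked to evaluate this.

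**Debriefing.** Under CPM Decision Aid Arm Debriefing, staff at two sites "will contact current and former participants from the B-sure decision aid arm" to seek consent for a call in which "The interviewer will remind participants of the information included in each of the B-Sure decision aid modules". The detailed procedure that follows says that DA-arm women who "completed all aspects of the study will be approached for the debriefing interview". Section 4.2.2, after placing feedback collection at follow-up 1, adds that "we may also contact participants by phone for a short debriefing on their experience with the site".

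**Analysis.** Section 5.2 compares outcomes between arms by repeated measures and intention to treat, and labels this exploratory. It mentions neither website tracking nor debriefing.

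**The concern.** Two exposures exist in the DA arm only, and both would push its knowledge score upwards.

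The first is the open website. A woman at home with her survey and her log-in can answer with the teaching material in view. The plan names this hazard but attaches no consequence to what the tracking finds: no time window, no rule and no sensitivity analysis.

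The second is the debriefing call. If it reaches a woman who has not yet returned follow-up 2, she hears a reminder of the module content before her last knowledge test. No Usual Care woman receives such a call.

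The knowledge result is preliminary evidence for a larger trial. The aid is meant to inform a choice that, by section 2.3, is made before mastectomy. Knowledge picked up after surgery in order to answer a survey generally cannot have informed that choice, but in the arm means it would look the same as knowledge that did.

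**Working it through.** The plan gives no power, effect size or standard deviation for knowledge, so there is no figure to reproduce. The check has two parts.

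**1. Can the debriefing call precede follow-up 2?**

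- The opening sentence covers current as well as former DA participants. A current participant may still owe follow-up 2, so this wording permits an early call.
- The detailed procedure limits the approach to women who have finished every part of the study. That includes follow-up 2, so under this wording a call cannot affect any knowledge score.
- Section 4.2.2 permits a phone debriefing and sets no time for it.

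An early call is thus neither planned nor excluded. The procedure is described for MSKCC and MGH only, but section 3.2.3 expects those sites to supply 90 + 30 = 120 of 130 women.

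**2. How large could look-up bias be?**

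Input from section 5.2: 85 women complete follow-up, or 85/2 = 42.5 per arm if allocation is equal.

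Assumptions, none from the documents: knowledge SD of 2 items; a share f of DA women look up answers and gain g items each; no true difference in retained knowledge; two-sided 5% test.

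- SE of the arm difference = SD × √(2/n) = 2 × √(2/42.5) = 0.434 items.
- Bias = f × g.
- Chance of a nominally significant result favouring the DA = Φ(bias/SE − 1.96).

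| f | g (items) | Bias (items) | Bias/SE | Chance |
|---|---|---|---|---|
| 0 | – | 0 | 0 | 2.5% |
| 5% | 3 | 0.15 | 0.35 | about 5% |
| 10% | 4 | 0.40 | 0.92 | about 15% |
| 20% | 4 | 0.80 | 1.84 | about 45% |

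A milder case in SD units: SE = √(2/42.5) = 0.217 SD. With 5% looking up and gaining 0.5 SD, the bias is 0.025 SD, or 0.025/0.217 = 0.12 SE, and the chance is 3.3%. That is negligible.

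The largest case is demanding. It needs 0.20 × 42.5 = 8.5 women who each gain 4 of 11 items, which is 4/2 = 2 SD.

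The documents offer nothing with which to size the effect of an early debriefing call, so none is given.

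**The case against.** The case for leaving the plan alone is substantial, and much of it stands.

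- **Usual Care women are not cut off from answers.** Home internet is an inclusion criterion for everyone (section 3.2.1). A reader might infer that only DA women can see the answers; that is true of the DA website, not of the information in general. Clinic and phone completion also limit look-up in both arms. Still, a general search is not the same as a log-in to modules written on these topics.
- **The risk was not ignored.** The plan states it and tracks use. What is missing is the link from tracking to analysis.
- **The debriefing is a feedback interview with separate consent.** A reader might infer that DA women are re-taught by phone, or that section 4.2.2 schedules the call before follow-up 2. The text supports neither: women are reminded of what the modules contained, and section 4.2.2 sets no time.
- **The outcome is exploratory.** No significance level is set, and no decision in the plan turns on it. Its place at the head of the list in section 5.2 is not a ranking; the secondary aim lists preparedness and decisional conflict before it.
- **The estimand matters.** If the question is the effect of having access to the aid, consulting the site is part of the intervention. The bias concerns retained knowledge, which section 5.2 does not separate from looked-up answers.

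Suspending log-ins while a survey is open is a tempting remedy but a debatable trade. It could disturb the usage measures that section 5.1 needs for feasibility and acceptability. It would not reach pages already printed or sent to a mobile device, which section 4.2.2 counts. The two-week contact rule in section 3.2.2 is discretionary and does not close a survey, so a lock-out could be open-ended.

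**Conclusion.** The point holds as a possibility, not as a demonstrated bias. Access to the aid is one-sided during unsupervised tests, the planned tracking has no role in section 5.2, and the debriefing text contradicts itself on who may be called and therefore when. The direction is clear: any look-up of DA content, or a reminder call before follow-up 2, would tend to raise the DA arm's score.

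The size is not known. On the assumptions above it runs from about 0.1 SE, which can be ignored, to about 1.8 SE, which would come close to nominal significance with no true effect. Nothing in the documents shows where in that range the trial would fall. A reader might conclude that the comparison does favour the DA; the documents support only that it could.

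The acceptance and retention criteria of the primary feasibility aim are unaffected. This is a low-cost improvement to a secondary comparison, not a flaw in the trial's main purpose.

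**What to change.** 1. **Debriefing.** Reconcile the two statements under CPM Decision Aid Arm Debriefing, and section 4.2.2, so that no debriefing call takes place until follow-up 2 has been received or closed. State what closes a survey.
2. **Closed-book instruction.** Put the same sentence above the knowledge items in both follow-up surveys and both arms, asking women to answer without consulting the website, printed pages or other sources. It cannot be enforced, but it also covers printed material and Usual Care searches, and it leaves log-ins and usage measures untouched.
3. **Section 5.2.** Keep the full intention-to-treat knowledge comparison as the main result. Pre-specify one sensitivity analysis that repeats it without surveys that had a DA log-in between issue and return. Say in the plan that this selects on behaviour after randomisation, in one arm only, and that a log-in is not proof of look-up. It shows how far the result depends on those surveys and does not correct it. Record issue date, return date and survey mode.

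Cost: a wording amendment, one added survey sentence and slightly more analysis. Debriefing feedback from women still in follow-up would arrive later.

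### Study staff assign from a blocked master file and every allocation is announced to all sites, so allocation concealment is not assured

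*Combined protocol and SAP*

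**What the plan says.** The Randomization Procedures part of section 3.2.2 gives the sequence of steps:

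- Design and oversight: "A Rutgers CINJ statistician will design a blocked randomization scheme and will also ensure that randomization procedures are being followed".
- Site staff tell the main site when a consent and baseline have arrived. The Rutgers coordinator or other appropriate staff there "will randomize from the master file in the order in which notification of a new consent/baseline packet was received".
- Afterwards, "The master file will be updated and research staff at all sites will be notified of the randomization".
- Timing: "Patients will be assigned to condition after consent is acknowledged online or paper consent is signed" and the baseline packet is complete.

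Other sections show who has discretion before that moment:

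- Under recruitment in 3.2.2, the surgeon refers a woman judged to be considering CPM. Then "The project coordinator or designated study staff will review eligibility with the surgeon and medical staff", and the same staff explain the study and go through consent.
- Also in 3.2.2, Massachusetts General women sign consent before eligibility is verified, baselines may come back by mail, email or fax, and recruiters and site investigators meet every two weeks about accrual.
- Section 3.5 has a Rutgers Program Coordinator work with each site on the signed eligibility checklist.
- Section 3.2.3 plans "90 MSKCC, 10 CINJ, 30 MGH", with 65 women per arm.

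No section says that unused rows are hidden, who may open the master file, or that notices go only to the enrolling site.

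**The concern.** In a blocked list, past allocations carry information about the next one. Sending each result to all three sites gives everyone the full history of the list. Anyone able to open the master file might see the coming rows as well.

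Allocating after consent and baseline stops a woman being moved once her arm is known. It does not stop earlier choices made in the light of a likely next arm: whether she is referred or approached, how a borderline eligibility question is settled, and when her packet is notified. Notification order fixes the arm, so timing alone can change it.

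The arm comparison in section 5.2 is exploratory, but its estimates are the preliminary data for further research. Section 5.1 also judges the decision aid, under the primary aim, by use (75% of participants using it, more than 75% of pages reviewed) and by a mean evaluation above 5.6 out of 7. Those results come only from women given the aid. The same section names younger age, internet familiarity and higher education as possible correlates of use, and recruiters may be able to observe or infer some of these. Steering likely users into that arm would flatter the criteria.

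**Working it through.** The plan gives no predictability figure, so there is none to reproduce. Inputs are 1:1 allocation, N = 130 and sites of 90, 30 and 10 (section 3.2.3). Block size b is not stated; I assume 2 to 10.

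**1. Full history known, woman takes the next slot, fixed block size known.** The best guess is the arm that is behind within the block.

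- Share of assignments known with certainty = 2/(b + 2).
- Share guessed correctly = 1/2 + [2^b / C(b, b/2) − 1] / (2b).

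Example, b = 4: certain = 2/6 = 33%; correct = 0.5 + (16/6 − 1)/8 = 0.5 + 0.208 = 71%. Enumerating all balanced blocks gives the same values.

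| b | Certain | Of 130 | Correct |
|---|---|---|---|
| 2 | 50% | 65 | 75% |
| 4 | 33% | 43 | 71% |
| 6 | 25% | 33 | 68% |
| 8 | 20% | 26 | 67% |
| 10 | 17% | 22 | 65% |

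Full concealment gives 0% certain and 50% correct.

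**2. Full history known, block sizes random and undisclosed.** Guessing the arm that is behind overall (simulation, N = 130): blocks 2/4/6, 70%; 4/6, 69%; 4/6/8, 68%. Varying the block size does not cure the all-site notice.

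**3. Each site sees only its own allocations from one common list.** Two guessing rules matter.

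- *Simple rule: guess the arm behind in the site's own count.* Simulation gives 54–55% at the 90-woman site, 52% at the 30-woman site and 51% at the 10-woman site.
- *Best rule, with block size and slot known (like for like with step 1).* Let h = b/2 and let p be the chance that an earlier slot in the block is the site's own (89/129, 29/129, 9/129). With i earlier slots in the block, the site sees m ~ Bin(i, p) of them. Of these, x are in the decision-aid arm with probability C(h, x)·C(h, m − x)/C(b, m). The next slot is then in that arm with probability (h − x)/(b − m), and the more likely arm is guessed. For b = 2 this is 0.5 + 0.25 × 89/129 = 67%.

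| b | 90-woman site | 30-woman site | 10-woman site |
|---|---|---|---|
| 2 | 67% | 56% | 52% |
| 4 | 63% | 55% | 52% |
| 6 | 61% | 54% | 52% |
| 8 | 60% | 54% | 52% |
| 10 | 59% | 54% | 52% |

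Stopping cross-site notices therefore helps the two smaller sites most. At the largest site the gain against a well-informed guesser is 6 to 8 points, which is why undisclosed block sizes are needed too.

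**4. Blocks made within site, with own-site notices.** Each site again holds a complete block history. With random sizes (2/4, 2/4/6, 4/6, 4/6/8) the simple rule gives about 66–72%; fixed sizes known to staff give the 65–75% of step 1. Most of the gain in step 3 is lost.

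**5. Sight of future rows.** Anyone who can open those rows knows every assignment, whatever the block size.

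**The case against.** The strongest reply has five parts.

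- **Allocation is central.** For 90 + 30 = 120 of 130 women the list is held away from the enrolling site, and a statistician checks adherence. This stands as a partial safeguard. A reader might infer that the person who recruits also draws the assignment. The documents do not say so: the project coordinator in the recruitment text, the Rutgers coordinator in the randomisation text and the Program Coordinator in section 3.5 are not identified as one person. What is stated is that Rutgers staff randomise, and that Rutgers also recruits and takes part in eligibility sign-off. Oversight of procedure does not itself hide the list.
- **Certainty is not shown.** A reader might conclude that upcoming assignments can simply be predicted. That needs a known block size or sight of future rows, and the plan states neither. Otherwise prediction is only partial.
- **The guess rates are upper bounds.** Referral and approach come well before notification, and packets from three sites share one queue. If one allocation unknown to the guesser intervenes, correct guesses fall from 75% to 50% (b = 2), 71% to 58% (b = 4) and 68% to 60% (b = 6). This stands. The higher rates fit the timing of notification better than the choice of whom to approach.
- **Enrolling sites need their own women's arms.** The process evaluation at follow-up 1 is for the decision-aid arm only, and Memorial Sloan Kettering and Massachusetts General staff contact women in that arm for debriefing. This also stands, so only the cross-site notices lack a stated purpose.
- **The comparison is exploratory.** True, and it limits the consequence. It does not remove the possible effect on the use and acceptability criteria.

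**Conclusion.** The point holds in this form: as written, the procedure does not assure concealment, and the all-site notice makes matters worse than the trial needs. With the full history and the next slot known, correct guesses reach 65–75% for blocks of 10 to 2. With own-site notices on one common list they are 51–55% under the simple rule, and at most 59–67% at the largest site.

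These figures assume 1:1 permuted blocks, complete blocks and a guesser who tracks allocations. They measure the opportunity for selection. They do not show that selection would occur, and no size of bias in any outcome can be derived from the documents.

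Two further readings are not supported. The unstated block size is missing detail, not evidence that staff know it. The absence of stated site strata is not a flaw here: chance imbalance between sites is a different matter from selection bias, and stratified blocks would raise predictability. The change should be made because it is cheap, but the consequence is moderate.

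**What to change.** Amend Randomization Procedures in section 3.2.2 to say that:

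1. the statistician or a restricted-access system holds the list and releases one assignment at a time, after eligibility, consent and baseline are all confirmed;
2. staff who approach women or sign off eligibility, at any site including Rutgers, cannot view the list;
3. each allocation goes only to the enrolling site and to the staff who inform the woman;
4. block sizes vary and are not disclosed to recruiting staff;
5. one common list is kept across sites.

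The Rutgers staff who inform women from all sites will still know the whole history, so they should not be the people covered by item 2. If some of these safeguards already operate, writing them into the section settles that part.

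The cost is a small one-off set-up of access rights and a short delay in releasing each assignment. Keeping one list accepts some chance imbalance between arms within a site. With surgery scheduled within one to three weeks (section 2.3), release needs a named back-up so that the delay stays short.
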